## 6.3 Efficacy testing of nets with a mixture of insecticides

The benefits of novel non-pyrethroid insecticidal nets that withstand fewer than 20 standard washes but meet the grave threat of pyrethroid resistance may have to be considered. It is anticipated that novel LLINs products will contain mixtures of at least two unrelated insecticides. 'Mixtures' are products in which at least two insecticides are co-formulated, such that an insect on contact is exposed to both insecticides at the same time. In all cases, the efficacy, wash-resistance and regeneration of the candidate LLINs should be determined for both the product as a mixture and for the individual components of the product. This is necessary in order to understand and demonstrate the benefit of combining them. The following modifications in the studies are recommended for LLINs products with mixtures of insecticides: At the begining testing should be conducted against both a susceptible and one or more pyrethroid-resistant mosquito strains. The regeneration time and washing interval should be those of the final product. The following treatment arms are recommended for LLINs in which two compounds in the mixture are active against mosquitoes, in order to determine the efficacy of the individual insecticides and the added benefit of the mixture: Candidate LLINs with compound A only or candidate LLINs with compound B only.

The trials should initially be conducted in an area with mosquitoes susceptible to both pyrethroids and the compounds in the mixture in the candidate LLINs. If the product is as effective as the reference LLINs, it should also be tested in an area with pyrethroid-resistant mosquito populations that show reduced mortality and blood-feeding inhibition when conventional LLINs with pyrethroid are used. The following treatment arms should be tested: An untreated net, preferably of the same material as the candidate LLINs; if not available, possibly a polyester net. Candidate mixture LLINs, unwashed, candidate mixture LN, washed 20 times, reference LN, unwashed and reference LN, washed 20 times.

The ultimate decision is based on a comparison of the candidate LLINs washed 20 times and the positive control washed 20 times. The efficacy of the candidate LLINs in terms of mortality and blood-feeding inhibition should be equal to or better than that of the positive control. Bioassays of nets before washing, after washing and after the field trial should be done with colony mosquitoes as well as with wild-caught pyrethroid-resistant mosquitoes. As noted above, mosquitoes collected in the field should be additional treatment arms may be required if more than two compounds are present in the candidate LLINs. If removal of one compound from the candidate LLINs significantly alters the migration or release of the other compound, conventionally treated nets might have to be included to test each compound individually (arms 2 and 3). The benefits of novel net products with mixtures of insecticides that withstand fewer than 20 standard washes but meet the grave threat of pyrethroid resistance will be considered, preserved for quality control or future studies of genetic markers of insecticide resistance and their relation to efficacy. The studies should include at least two LLINs products: the candidate LLINs and a reference LLINs. It is not necessary to test the component parts of the candidate LLINs separately. It is recommended that both pyrethroid-susceptible and pyrethroid resistant mosquitoes be tested in WHO bioassays and tunnel tests.

## 6.4 Efficacy testing of combination nets

Combination LLINs contain two or more different nettings, each of which has a different specification for fibres and/or active ingredient(s), with or without synergists. In case of trials each netting component must be assessed separately. The full product should be studied. When the netting contains a mixture of insecticides or insecticide plus a synergist, the principles for evaluating LLINs with mixtures as described above generally apply. The full product should be compared with a reference LLINs, but bioassays should be conducted separately on each netting component of the LLINs. Depending on the specifications of the net, the sampling scheme for bioassays and chemical assays may require modification of both type of testing procedure.

# 7. LLINs study statistical analysis

Analysis of variance Chi-square and t-test statistics will be used as appropriate to compare mosquito mortality between the different test series to evaluate the potential of LLINs with WHO cut off criteria. Other appropriate optional software can be used for the analysis.

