### 5.3.1 In case I

Each net will be tested for wash resistance and bio-efficacy once every two months for a total of 12 months (this is case I). The bimonthly washing and bio-efficacy will be conducted in two groups:

- a) Washing to be conducted by trained persons using the standard procedure with close supervision,
- b) Washing to be conducted by the users themselves by instructing them with the method of washing.

Each net will be washed using the protocol described above, according to the schedule outlined in Table 1. Standard WHO cone bioassay will be performed on 30 randomly selected nets of each type at the start of the project and every two months for bioassay, wash resistance and physical inspection. The bioassay will be performed according to the established regeneration time for each net type thereafter cones will be placed in sub sampling locations on each net as shown in Annex 2.

Five susceptible, non-blood fed, two to five day old female susceptible *Anopheles arebiensis* mosquitoes exposed to the net for three minutes, after which they are held for 24 hours with access to the sugar solution. At least 50 mosquitoes on each net (10 replicates) and samples from different type of nets will be tested.

The results will be reported for each net tested along with the pooled results (5 x  $10 \times 4 = 200$  mosquitoes). The number of mosquitoes KD will be counted 60 minutes after exposure, and mortality (functional and effective) after 24 hours of recovery period will be recorded. An average mortality and KD value for each treatment group will then be calculated based on the number of nets for each group (WHO, 2013.1). Bioassay data for each of the sub-sampling locations on the net will also be analysed separately to see if there is a specific trend which may be indicative of more insecticide loss in lower parts of the net due to physical abrasion or lower and central parts of the net due to physical handling. Mosquitoes exposed to untreated nets will be used as controls. If mortality for a given day is between 5% and 20% on the control net it is corrected by an Abbot's formula, if mortality for a given day is > 20% all bioassays carried out on that day will be repeated. The same mosquito strain will be used throughout the study.

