#### 5.3.2 For case II

The same *Anopheline* species and same procedure implemented in all cases regarding cone bioassay, following the regeneration of the insecticide or bioavailability given by the manufacturer. The bioassay will be carried on randomly selected 30 sample nets from each type every six months. At the end of three years, at least 80% of nets meet the cut off criteria for either the WHO cone bioassay test or the tunnel test, and then the product meets the definition for a LLINs.

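### Section 7 lists chi-square for mosquito mortality without making the net the unit of analysis, and the pooled count of 200 in 5.3.1 is not reconciled with 30 nets

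*Protocol*

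**What the plan says.** Protocol Section 7 gives the whole analysis plan for the bioassay data in one sentence. It names three tests: "Analysis of variance Chi-square and t-test statistics will be used as appropriate to compare mosquito mortality between the different test series". The stated aim is "to evaluate the potential of LLINs with WHO cut off criteria". It gives no unit of analysis, significance level or between-net variance.

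The data structure is in Section 5.3.1. For Case I, "Standard WHO cone bioassay will be performed on 30 randomly selected nets of each type at the start of the project and every two months". On each net, five mosquitoes are exposed per cone: "At least 50 mosquitoes on each net (10 replicates) and samples from different type of nets will be tested". Section 5.3.2 uses the same cone procedure in Case II: "The bioassay will be carried on randomly selected 30 sample nets from each type every six months".

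On reporting, Section 5.3.1 says "The results will be reported for each net tested along with the pooled results", and gives the pooled number as 5 x 10 x 4 = 200 without saying what the 4 stands for. It then describes a net-based summary: "An average mortality and KD value for each treatment group will then be calculated based on the number of nets for each group".

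The pass/fail rules in 5.3.1 and 5.3.2 ask whether at least 80% of nets meet the cut-off. Sections 4.2 and 4.3 mention between-cluster, between-net and between-household variation, but only for sample size.

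**The concern.** Mosquitoes tested on one net share its insecticide content, wash history, household and usually its test day. Their outcomes are therefore correlated. A chi-square test on pooled dead/alive counts treats every mosquito as independent, so it overstates precision whenever nets of the same type differ in true mortality.

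Section 7 names mosquito mortality as the outcome and chi-square as one of the tests, and 5.3.1 plans pooled results. An analyst could follow the text as written and run that test. The comparisons at risk are those of mortality between test series or products. These include candidate against reference nets in Sections 6.2 and 6.3, if a significance test is used there. Section 2 gives the choice of nets for procurement as one use of the results, so a spurious difference could matter.

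The pooled count of 200 adds to the uncertainty. A reader cannot tell how many nets or mosquitoes stand behind a pooled result.

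**Working it through.** **Pooled count**

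- Printed figure: 5 x 10 x 4 = 200. The multiplication is correct.
- Per net (5.3.1): 5 mosquitoes x 10 replicates = 50, stated as a minimum.
- Per net type per round: 30 nets x 50 = 1,500, again a minimum.
- If the 4 means nets: 200 / 50 = 4 nets, which does not match 30.
- If the 4 means positions on one net: 4 x 50 = 200 per net, and 30 x 200 = 6,000 per net type per round. This does not match 10 replicates per net.

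Neither reading makes 200 the pooled total for 30 nets.

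**Type I error of a mosquito-level chi-square**

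Inputs from the protocol: 30 nets per type and 50 mosquitoes per net. Assumptions, because the protocol gives none: two-sided alpha of 5%, and an ICC range of 0 to 0.20.

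Design effect: DEFF = 1 + (50 - 1) x ICC.

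Under no true difference, the pooled test statistic has variance DEFF instead of 1. The actual type I error is therefore 2 x [1 - Phi(1.96 / sqrt(DEFF))], and the effective number of mosquitoes is 1,500 / DEFF.

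Example at ICC 0.02: DEFF = 1 + 49 x 0.02 = 1.98; 1.96 / sqrt(1.98) = 1.39; type I error = 16.4%.

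| ICC | DEFF | Type I error | Effective mosquitoes out of 1,500 |
|---|---|---|---|
| 0 | 1.00 | 5.0% | 1,500 |
| 0.005 | 1.245 | 7.9% | 1,205 |
| 0.01 | 1.49 | 10.8% | 1,007 |
| 0.02 | 1.98 | 16.4% | 758 |
| 0.05 | 3.45 | 29.1% | 435 |
| 0.10 | 5.90 | 42.0% | 254 |
| 0.20 | 10.80 | 55.1% | 139 |

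Solving the formula backwards, the error reaches 10% at an ICC of about 0.009 and 15% at about 0.017.

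**Check by simulation**

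Two identical products were simulated with beta-binomial mortality, 30 nets each, 50 mosquitoes per net and 20,000 runs per setting.

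| ICC | Pooled chi-square, true mortality 80% | Pooled chi-square, true mortality 90% |
|---|---|---|
| 0 | 4.9% | 5.0% |
| 0.01 | 10.9% | 10.5% |
| 0.02 | 16.1% | 17.1% |
| 0.05 | 28.8% | 29.0% |
| 0.10 | 42.2% | 42.0% |
| 0.20 | 55.4% | 54.6% |

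A t-test on the 30 per-net proportions in each group rejected in 4.7% to 5.2% of runs across all these settings.

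**Link between the two parts**

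If 200 were meant per net, DEFF would be 1 + 199 x ICC. The pooled chi-square error would then be 25.7% at ICC 0.01 and 38.0% at ICC 0.02. The meaning of the 4 therefore affects the size of the problem.

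**The case against.** The strongest reply is that the protocol does not commit to the faulty analysis. Section 7 lists three tests and leaves the choice to suitability. A t-test or ANOVA on per-net mortality is valid, and 5.3.1 already reports results per net and averages over nets. The unit of analysis and any random effects are often left to a statistical analysis plan, and one may exist here. All of this stands. A reader might infer that the plan fixes chi-square on pooled mosquitoes; the text does not say so. What remains is that Section 7 names a test that, in its most direct use on this outcome, ignores the nesting described in 5.3.1, and nothing in the protocol rules that use out.

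It is also true that the LLIN decision in Cases I and II rests on a count of nets, with no mosquito-level test, and that Sections 6.2 and 6.3 state no significance test for the comparison with the reference net. A reader might infer that pass/fail results would be distorted, or that products would be ranked on noise. The protocol does not support either: the 80% rules already use the net as the unit, and no ranking rule based on p-values is given.

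Finally, the ICC is unknown. One strain tested under controlled temperature and humidity could give a low value. At ICC 0.005 to 0.01 the error is about 1.6 to 2.2 times nominal, so an unconditional claim of several-fold inflation goes too far.

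**Conclusion.** The point holds conditionally. Section 7 leaves the unit of analysis open and permits a chi-square test that does not fit a design with at least 50 mosquitoes per net. If that test is run on pooled counts, a nominal 5% error becomes about 8% at ICC 0.005, 11% at 0.01, 16% at 0.02, 29% at 0.05 and 42% at 0.10. These figures rest on an assumed two-sided 5% level, exactly 50 mosquitoes per net, 30 nets per group and an assumed ICC. They describe within-net clustering only; shared households or test days are not modelled. The effect is confined to mortality comparisons between test series or products.

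The count of 200 is a separate inconsistency. A reader might infer that it is an arithmetic slip, or that it can only mean four nets and should simply read 1,500. Neither follows. The multiplication is right, and the 4 could also mean four positions on one net: Section 5.5.1 refers to positions 1 to 4 in Annex 2, and the Annex 2 diagram is not in the text available for this review. What can be said is that the 4 is undefined and that 200 cannot be the pooled total for 30 nets.

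**What to change.** In Section 7:

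- State that the net is the unit of analysis for mosquito mortality and knock-down.
- Compare groups by t-test or ANOVA on per-net proportions, in line with the net-based averaging in 5.3.1, or by a logistic mixed model or generalised estimating equations with net as the cluster.
- State that chi-square will not be applied to pooled mosquito counts. It can still be used where each net contributes one pass/fail result.

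In Section 5.3.1, define the factor 4 and reconcile 200 with 30 nets of at least 50 mosquitoes: at least 1,500 per net type per round, or 6,000 if 200 is meant per net.

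The 80%-of-nets rules need no change for this reason.

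The cost is wording and slightly more analysis work on the same data. Intervals will be wider than those from a pooled analysis by a factor of about sqrt(DEFF): sqrt(1.49) = 1.2 at ICC 0.01, sqrt(1.98) = 1.4 at 0.02 and sqrt(3.45) = 1.9 at 0.05. That extra width is the uncertainty that pooling would hide.

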# 8. LLINs project budget breakdown

For Evaluating LLINs project currently 90,000.00 USD is estimated and detail budget breakdown is maintained in the Memorandum of understanding and it also possible to revise it based on the recent situation at the time of signature of agreement document.

# 9. LLINs project ethical considerations

The WHO and independent risk assessment of pesticide products have to show that the LLINs are safe to use; all study participants will be provided with a new net free of charge at the end of the study. The purpose of the study will be explained and householders will be asked to participate for the duration of the study. The head of each household will be asked to complete an informed consent form, which will be explained in the local language and read aloud if the person is illiterate (Annex 4). Scientific and Ethical Review Office of Ethiopian Health and Nutrition Research Institute will also approve the protocol and informed consent will be obtained from the study participants.

# 10. LLINs project reporting

Outcomes should be communicated to the community, to relevant national programme, other stakeholders and to the manufacturers. Investigators are also encouraged to publish the results of these studies in peer-reviewed journals.

# 11. Publication policy

We at EPHI, aspire to select research paper, through highest quality peer review. To achieve this, the entire peer review and publication process must be thorough, objective, and fair. Almost every aspect of this process involves important ethical principles and decisions, which are seldom explicitly stated and even less often shared with the readership. Journal's reputations depend on the trust of readers, authors, researchers, reviewers, editors, research subjects, funding agencies, and administrators of public health policy. This trust is enhanced by describing as explicitly as possible the journal's policies to ensure the ethical treatment of all participants in the publication process. We have been following Publications Guidelines.

We at EPHI aspire to select research paper, through highest quality peer review. Publications should strictly seek original work that has not been previously published or currently not under review at another journal or conference.

# 12. LLINs project implementation protocol by Phase

	List of activities by phase	Duration	
Phase	Activities	Commencement	Completion
Phase 1	Project proposal development and Finalization	June 1	June 30
Phase 2	Memorandum of understanding to conduct the bio efficacy test	July 1	July 15
Phase 3	Procurement of nets and other essentials	July 1	July 30
Phase 4	Field evaluation of nets and Chemical analysis	August 1	May 30
Phase 5	Data entry and analysis for wash resistance	January 1	May 15
Phase 6	Case I or 12 months report	May 1	May 30
Phase 7	Case II final technical report	May 30/2019	
The total time required		3years	

The end date of LLINs project will be revised based on the starting date of data collection and it is possibly rescheduled based on the working physical year.

# 13. LLINs project Benefits

The protocol serves as a guide to evaluate LLINs under the local conditions of Ethiopia, which will eventually be used in the malaria control programme and regulatory procedure.

# Information on physical status of the net sampled and its use

1. ID No
2. Date (DD/MM/YY)
3. Region
4. Zone
5. District
6. Kebele
7. Name of the interviewee
8. Sex 1) Male 2) Female
9. Age
10. Marital status 1) Married 2) Single 3) Other
11. Educational level
1) Illiterate 2) Can read and write 3) Grade 1-4
4) Grade 5-8 5) Grade 9-12 6) above grade12
12. Occupational status?
1)Housewife 2) Farmer 3) Merchant 4) Daily laborer 5) Government employee 6) Factory worker 7) student 8) seeking a job 9) Other
1) House with separate bedroom and kitchen
2) Tukul with kitchen /bedroom together
3) Other
14. For how long have you usedthe bed net?
15. Do you have bed net? 1) Yes 2) No
16. If yes, type of the bed net 1) Circular 2) Rectangular 3) Combination
17. Number of nets
18. Can you tell me the age of each bed net? (Write from old to the recent one)
18.1. Bed net one
18.2. Bed net two
18.3. Bed net three

19. Usually where do you place the bed net?			
1) Bedroom 2) Kitchen 3) Entrance room 4) Other			
20. Do you use the bed net?			

 
Every night
 
Occasionally
 
			
3. Other			
21. Where do you keep the bed net during day time? (Observation)			

 
Hanged daily
 
Lift up
 
			
3. Stored away daily			
22. Where is the location of the bed net today? (Observation)			

 
Stored (cupboard / suitcase etc.)
 
Hanging but not ready for use
 
			
3. Hanging ready for use			
4. Other			
23. Observe and ask how do they hang the bed net? (Observation)			

 
Hanging over the bed to the floor
 
Hanging over the bed tucked in
 
			
3. Hanging over sleeping mat/mattress on the ground			
4. Other			
24. What type of bed do you have?			
1)Pole and rope 2)Wooden planks 3)Metal spring 4)Mat or other floor covering			
5)Other			
25. Has any one of your bed net been washed?			
25.1. Bed net one 1) Yes 2) No			
25.2. Bed net two 1) Yes 2) No			
25.3. Bed net three 1) Yes 2) No			
26. For how many times?			
26.1. Bed net one Times			

26.2. Bed net two Times
26.3. Bed net threeTimes
27. How often do you wash the net?
27.1. Bed net one
1) Once/year 2) Twice/ year 3) Three times/year 4) Four times/year
5) Never washed 6) other
27.2. Bed net two
1) Once/year 2) Twice/ year 3) Three times/year 4) Four times/year
5) Never washed 6) other
27.3. Bed net three
1) Once/year 2) Twice/ year 3) Three times/year 4) Four times/year
5) Never washed 6) other
28. Can you tell me the temperature of the water used to wash the bed net?
1) With cold water 2) With warm water 3) With hot water
29. Can you tell me the type of detergent or soap used to wash your bed net?
1. Commercial soap
2. Commercial powder
3. Mixture of soap and powder soaking
4. Other
30. For how long do you washed the bed net at a time?
1) For less than an hour 2) For more than an hour
31) Do you rinse the bed net before drying?  1) Yes 2) No
32. Do you rub the bed net against the rock?  1) Yes  2) No
33. Where do you dry the bed net after washing?
1) Inside home 2) Outside home 3) other
34. To dry, how do you hang the bed net after washing?
1) Flat 2) Hanging
35. How do you dry the bed net? 1) Sun light 2) Shade 3) other

[figure not shown]
36. Does the bed net have holes	3;		
36.1. Bed net one 1) Yes	2) No		
36.2. Bed net two 1) Yes	2) No		
36.3. Bed net three 1) Yes	2) No		
37. If Yes, Use the following cod	le for size of holes:		

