# 5.3 Net washing

Before the start of the field study, local washing conditions will be assessed and areas where washing is deemed excessively harsh will not be eligible for inclusion. The frequency and method of washing under field conditions will also be carefully monitored during the study. If washing conditions prove excessively harsh during the trial the result will be weighed accordingly.

Nets will be washed by trained persons using a standard procedure each time following the standard WHO procedure. The nets will be washed in clean well water with a small quantity of local soap (Soap commonly available in the community; no more than two grams per litre of water). The nets will not be left in the water to soak for longer than 10 minutes and agitated gently for no more than 5 minutes by hand, and the samples should be removed and rinsed twice for 10 minutes in clean water in the same shaking condition as stated above then dried horizontally in the shade. The PH of the water will be recorded. At the same time the Participant will wash their LLINs according to the method of washing following standard WHO procedure on the basis of washing schedule shown in Table 1.

Table 1. Washing schedule

Number of washes	Months of use
Baseline	0
1 wash	2
2washes	4
3washes	6
4washes	8
5washes	10
6washes	12

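### Annex 1 item 30 splits wash duration only at one hour, and no item asks soaking time or soap amount, so the questionnaire cannot show whether user washing kept to the limits in section 5.3

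*Protocol*

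**What the plan says.** Protocol section 5.3 (Net washing) sets the field wash. Nets are not to be left "to soak for longer than 10 minutes and agitated gently for no more than 5 minutes by hand", and are then "rinsed twice for 10 minutes in clean water". Soap is limited to 2 g per litre.

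The same section makes two commitments: "The frequency and method of washing under field conditions will also be carefully monitored during the study", and "If washing conditions prove excessively harsh during the trial the result will be weighed accordingly".

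Section 5.3.1 splits Case I washing into (a) trained persons under close supervision and (b) users who have been instructed in the method. Washing follows Table 1, which reaches six washes at month 12.

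Annex 1 is the only questionnaire shown, and section 5.1.1 names it for each Case I visit. Its washing items are:

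- Items 25 to 27, per net: whether washed, how many times (an open number), and how often. The named frequencies are "1) Once/year 2) Twice/ year 3) Three times/year 4) Four times/year", followed by a never-washed option and a residual option.
- Items 28, 29 and 31 to 35, asked once per interview: water temperature, type of detergent or soap, rinsing, rubbing against rock, and the place, manner and sun or shade of drying.
- Item 30, also asked once: the duration of a wash, answered "1) For less than an hour 2) For more than an hour".

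**The concern.** The limits in section 5.3 are 10 and 5 minutes; the only time question in the form has a single cut at 60. If every wash that respects the limits gets the same code as many that break them, item 30 says almost nothing about adherence. Two of the regulated quantities, soaking time and soap amount, are not asked about at all.

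This matters where users do the washing. The second specific objective (section 3.2) is wash resistance under repeated community washing, and Case I group (b) supplies it. In Case II, nets are in household use for three years, and section 5.3.2 does not restrict its decision to nets washed by trained persons. If activity is lost there, a reader will want to know whether the nets were washed within the limits. Section 5.3 says the result will be weighed if washing was harsh, but the answers on duration and soap would not support that. Information not collected at the visits cannot be recovered in the analysis.

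**Working it through.** **Inputs** (Protocol): soak at most 10 min, agitation at most 5 min, two rinses with a stated 10 min (section 5.3); single cut at 60 min (Annex 1, item 30); washing "once every two months for a total of 12 months" (section 5.3.1); six washes at month 12 (Table 1).

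**Step 1, the schedule.** 12 months / 2 months per wash = 6 washes, which reproduces Table 1.

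**Step 2, the longest compliant wash.** The rinsing text can be read two ways.

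- Two rinses of 10 min each: 10 + 5 + 2 × 10 = 35 min.
- Two rinses totalling 10 min: 10 + 5 + 10 = 25 min.

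Item 30 does not say whether soaking and rinsing count. If rinsing is left out, the maximum is 10 + 5 = 15 min. On every reading a compliant wash is below 60 min and takes the first code.

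**Step 3, what else takes the first code.** Keep rinsing as prescribed and ask how long soaking plus agitation can last before the whole wash reaches an hour.

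- With 20 min of rinsing: 60 − 20 = 40 min, against 15 allowed (40 / 15 = 2.7 times).
- With 10 min of rinsing: 60 − 10 = 50 min, against 15 allowed (50 / 15 = 3.3 times).

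Any wash below these totals is coded like a compliant one. Item 30 can reveal a breach only once the wash exceeds an hour, and even then it does not say whether the soak or the agitation was too long.

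**Step 4, each limit against the form.**

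| Element of the wash in section 5.3 | Annex 1 item |
|---|---|
| Soak at most 10 min | none |
| Agitation at most 5 min | item 30 only, cut at 60 min |
| Soap at most 2 g per litre | none (item 29 asks type, not amount) |
| Rinsing | item 31 (yes/no) |
| Drying flat, in shade | items 34 and 35 |

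**Step 5, the wash count.** Six washes can be recorded: item 26 takes any number per net, and item 27 has its residual option. Item 26 gives no reference period. Read as a cumulative total, which is its natural sense after item 25, the month-12 answer for an on-schedule net is 6; read as since the last visit, it is 1. The form also does not separate scheduled washes from extra ones, although section 5.1.1 tells Case I households not to wash their nets themselves.

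**The case against.** A fair opponent would make four points.

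- **The form does register harsh washing.** A reader might infer from item 30 that Annex 1 cannot identify it at all. That is not supported. Items 28, 29, 31, 32 and 35 record hot water, detergent type, missing rinses, rubbing on rock and sun drying. This stands, and it confines the point to duration, soaking and soap amount.
- **The frequency scale is adequate.** A reader might infer from the four named frequencies in item 27 that the six scheduled washes cannot be coded. They can, as Step 5 shows, and the number of scheduled Case I washes is fixed by Table 1 anyway. What remains is a wording matter in item 26.
- **The Case I evaluation does not rest on recall.** Section 5.3.1 bases it on cone results from nets washed by trained persons. This stands: poor user washing would not change that evaluation. It does not cover group (b) as evidence for the community-wash objective, or Case II.
- **Annex 1 is not expressly given this task.** Section 5.1.1 cites it for net use history, and the monitoring sentence in section 5.3 cites no form. Section 5.3 also provides a pre-study check of local washing and a record of water pH, and a separate wash log may exist. This lowers the weight of the point. But Annex 1 does ask about washing in detail, and on duration it does so with a cut that cannot serve the limits.

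One might also set the hour in item 30 against the 5-minute agitation limit and quote a 12-fold excess. That would treat the whole recorded hour as agitation, which neither item 30 nor section 5.3 supports.

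**Conclusion.** The point holds in a narrow form. Item 30 cannot show whether the 10-minute soaking and 5-minute agitation limits were kept, because a compliant wash takes at most 25 to 35 minutes and the only cut is at 60. Soaking time and soap amount are not asked. The consequence is limited to user-washed nets: Case I group (b) and routine washing in Case II. For these, adherence to the time and soap limits, and that part of the harsh-washing provision, cannot be judged from the questionnaire.

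This rests on two assumptions: that no other wash record covers these quantities, and that Annex 1 is also used at the six-monthly Case II visits, which section 5.1.2 does not say. The point is a cheap improvement to data collection. It does not threaten the Case I evaluation.

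**What to change.** Edit Annex 1 as follows.

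- Replace item 30 with two questions, minutes of soaking and minutes of rubbing or agitation. Set the first cut-points at the limits in section 5.3 (10 and 5 minutes); the higher categories are the sponsor's choice.
- Add a question on the amount of soap used, so that it can be set against the 2 g per litre limit.
- Word item 26 as the number of washes since the last study visit, with scheduled and other washes entered separately.
- Record these answers per net where different products are allocated within one household, as section 4.2 allows. Where a household holds one product, a single answer is enough.
- State in section 5.3 which form serves the monitoring of washing, in Case II as well as Case I.

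The cost is a slightly longer interview, with no extra visits or tests. Recalled minutes and soap amounts will be approximate, so they can separate clear breaches from plausible compliance but not settle close cases. The edit does not define excessively harsh washing, which section 5.3 leaves open.
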